The purpose of this feasibility study is to demonstrate the safety and efficacy of the Nucleus 24 Multichannel Auditory Brainstem Implant (ABI, Cochlear Corp, Sydney, AUS) in children who do not have the diagnosis of neurofibromatosis type II (NFII), and who have either experienced failed cochlear implantation (CI) or have been unable to receive a CI secondary to cochlear or cochlear nerve disorders. These conditions can include: developmental or acquired cochlear nerve deficiency (CND), cochlear aplasia (Michel), post-meningitis cochlear ossification, or cochlear malformation. This study proposes to implant up to 10 pre-linguistic young children (18 mos to 5 yrs. of age) and 5 post-linguistic children (<18 yrs of age) with the Nucleus 24 Multichannel ABI in an attempt to demonstrate safety of the surgical procedure, tolerance of device stimulation, and the potential for auditory benefit beyond that experienced with their CI. This study will provide the preliminary experience for a larger scale clinical trial.

Regulatory Status of the Investigational Device

Data supporting the safety and effectiveness of the Nucleus 24 ABI were provided to the United States Food and Drug Administration (FDA) in March 2000, as part of a Premarket Approval Application. On July 21, 2000, the Agency's Ear, Nose and Throat (ENT) Advisory Panel unanimously recommended that FDA release the Nucleus 24 ABI for use by individuals with NFII above the age of 11 years. Cochlear Americas received a letter of approval from the Agency in October 2000 (PMA No P000015). The letter is enclosed.

The Nucleus 24 ABI features a multichannel electrode lead that terminates in twenty-one, 0.7 mm platinum disk-electrodes. The 21 platinum contacts are arranged on the surface of a silicone rubber pad in three rows of seven contacts and are surgically placed on the surface of the brainstem; specifically, on the surface of the cochlear nucleus.

Background and Rationale

According to Stone, "Hearing impairment strikes at the very essence of being human, because it hinders communication with others" (1). Children born deaf (i.e. pre-linguistic deafness) have severe delays in speech and language acquisition that can retard their social and emotional development, influencing educational and career attainment (2). The pre-linguistic deafened child seldom develops significant understandable speech, and is often socially stigmatized by those in the hearing world (3). Thus, individuals with untreated congenital deafness are often integrated into a separate "deaf community." Hearing impairment negatively impacts upon educational attainment, employment opportunities, income, healthcare utilization, and life expectancy (1, 4-15). As most deaf children are educated outside of the mainstream setting and ultimately achieve lesser levels of employment and income, lifetime losses for having untreated severe to profound hearing loss have been estimated at over \$1 million dollars per child (\$297,000 added expenditures) (16-18). By comparison, these lifetime costs are significantly higher than for near drowning (\$98,500), accidents from firearms (\$89,100), stroke (\$129,200), rheumatoid arthritis (\$130,500), and epilepsy (\$172,900), and are similar to those for the devastating illness of schizophrenia (\$295,000). In addition to cost, deafness also contributes to an increased risk for depression, anxiety, and physical dysfunction (7, 8 19-21). In summary, untreated deafness is a major disability that negatively impacts upon all aspect of life.

A CI is an auditory, neural stimulating prosthesis. These devices use a multiple electrode array that is inserted into the cochlea to electrically stimulate the auditory (i.e. cochlear) nerve in cases of severe to profound hearing loss. Using specialized speech processing and encoding strategies, these devices can restore sound awareness and significantly improve speech perception in both quiet and noise. Improved speech perception restores communication for adults and allows children to develop spoken language (22, 23). Thus, CIs alleviate many of the disabling effects of deafness described above. In addition to quality of life benefits, the cost-utility of this intervention is positive for both adults and children (24, 25).

The only absolute contraindication to CI is an absent cochlea or an absent cochlear nerve. In addition, patients at risk for lower levels of performance include those with anatomic conditions that adversely affect the electrode-neural interface such as developmental labyrinthine malformations and cochlear ossification and fibrosis secondary to meningitis. While the diagnosis of cochlear (i.e. Michel) aplasia is clear clinically, the diagnosis of cochlear nerve aplasia is made somewhat more challenging by the spatial resolution of current imaging modalities (26-29). Because of this uncertainty, the term cochlear nerve deficiency (CND) was coined to refer to the situation where the cochlear nerve is small or absent on high resolution magnetic resonance imaging (MRI), or where the bony cochlear nerve aperture and canal are small or absent on temporal bone computed tomography (CT). The clinical diagnosis of CND includes these imaging findings in the setting of profound hearing loss (29, 30). Auditory brainstem response testing that shows a present cochlear microphonic but absent neural waves can support the diagnosis (29).

In an effort to provide hearing to deaf children who have inner ear malformations, CND, or ossification from meningitis, CI has been undertaken over the years (30). This might be considered the standard of care today for those who desire spoken language communication. Results of these interventions suggest that most children with CND gain some sound awareness from these devices using higher levels of electrical stimulation. However, achievement of open set speech perception for the purposes of speech and language development has been largely unsuccessful, probably as a result of a poor electrode-neural interface and other associated conditions (30-33). In the study from our institution, only 19% of children with CND developed any open set speech perception using their CI, and none of these children were able to communicate using auditory-only information (i.e. all used some supplemental sign language).

The ABI is an electronic device designed to convert environmental sounds into electrical impulses that are delivered along a multiple electrode array situated in close proximity to the cochlear nucleus in the brainstem. In a manner similar to the cochlear nerve, the cochlear nucleus maintains some degree of tonotopic arrangement; thus, application of discrete electrical stimulation along certain spatial locations within the lateral recess of the 4th ventricle results in discriminable psychophysical frequency percepts (i.e. pitch). The ABI is indicated for patients where the cochlear nerve is absent or unavailable for stimulation bilaterally. Most commonly, adults and children with hearing loss secondary to NFII with bilateral acoustic (8th nerve) tumors have been the main group of patients implanted to date.

In general, outcomes from ABI can be described in terms of sound detection and speech perception abilities using closed- and open-set test materials with and without the addition of lip-

reading. In a recent review of 86 NFII patients implanted with ABIs, 13 did not respond to stimulation and 1 was explanted (34). Of the 60 patients with available 6-month data, mean open-set speech perception scores (CUNY sentences) using the implant alone, vision alone, and both the implant and vision on CUNY sentence were <10%, 30%, and nearly 55% correct. However, there was a wide range of auditory abilities, with some patients obtaining combined vision and sound scores of >90% correct (34). Thus, in patients with NFII, the ABI is an excellent enhancement to lip-reading. For individuals that have known only spoken language throughout their entire life, this connection to the speaking world is significant, and the importance of this communication enhancement should not be underestimated.

Experience with Auditory Brainstem Implantation in Patients without NFII

The effectiveness of ABI for patients without NFII has only recently been explored (35-43). Colletti et al. in Verona, Italy, have summarized their results of a group of *adult patients* with a variety of conditions (excluding NFII) that received an ABI between 1997 and 2007 (40). Results were compared to a group of 34 individuals with NFII implanted by the same surgeon. The duration of deafness ranged from 3.2 to 8.5 years ($X = 5.1$; $SD = 2.4$) for the NFII group and ranged from 1.2 to 19.8 years ($X = 9.6$; $SD = 5.9$) for non-NFII group. All non-NFII patients were implanted through a retrosigmoid craniotomy. NFII patients also required tumor removal prior to placement of the ABI.

After at least one year of device use, using audition alone, sentence recognition ranged from 10 to 100% ($X = 59\%$; Median = 53%; $SD = 21.34$) in the non-NFII group ($n = 48$) and from 5 to 31% ($X = 10\%$; Median = 16%; $SD = 15.21$) in the NFII group ($n = 32$). These values were significantly better ($p = 0.0007$) in the non-NFII subgroup. Table 1 below, adapted from Colletti et al (2009), shows the sentence recognition score (type not specified) outcomes for the various etiologies without NFII (40). Except for those adults with auditory neuropathy, sentence recognition scores in these adult patients are significantly better than in the patients with NFII.

TABLE 1. Open-set sentence recognition 1-10 yrs. after ABI.

Cause	No. Subjects	Range,	% X	SD	T versus NT	t test
Head trauma	7	32-80	62	57	23,41	$p = 0.005$
Auditory neuropathy	4	12-18	15	16	2,52	$p = 0.07$
Cochlear malformations	6	37-61	44	61	11,2	$p = 0.006$
Altered cochlear patency	31	34-100	60	64	19,81	$p = 0.0048$

x-mean; Med-median, sd-standard deviation, T-tumor (NFII), NT-non-tumor

Based on these results, the investigators concluded that adults with acquired conditions that are isolated to the cochlea or cochlear nerve such as otosclerosis (altered cochlear patency) and traumatic cochlear nerve avulsion are better candidates for ABI success than those individuals with NFII. They hypothesized that NFII and/or its treatment results in pathological changes in the brainstem and cochlear nuclei that might preclude good performance with an ABI. Similarly, congenital malformations and auditory neuropathy might produce central nervous system changes that are not conducive to the development of open set speech perception using an ABI, possibly as a consequence of long-term auditory deprivation.

In theory, children would be better candidates than adults for an ABI since they have substantial developmental plasticity and have no auditory memory that requires precise matching

of signals. Colletti and colleagues in Verona, Italy, have placed *ABIs in children* without NFII and have summarized their experience in 2008 (41). In that study, 26 children (17 in Verona; 9 in other countries) aged 14 months to 16 years received an ABI for different tumor and non-tumor diseases between 1996 and 2006. Etiologies included cochlear nerve aplasia with or without associated inner ear malformations (n=19), NFII (n=2), incomplete cochlear partition (n=2), auditory neuropathy (n=1), post-meningitis ossification (n=1), and temporal bone fracture with nerve avulsion (n=1). Fourteen children had a variety of other disabilities including: mild motor delay (n=8), learning disability (n=7), behavioral impairment (n=7), cognitive delay (n=8), language delay (n=6), and 2 with visual impairment. Six children received previous CIs with no auditory results. All were operated through a retrosigmoid craniotomy, and there was one reported major complication (detailed below). Results showed that all children consistently use their devices (avg. 8 hrs./day) and demonstrated gradual improvement in communication skills, showing more attention and interest in school and at home. From an auditory perspective, 20 pre-linguistic and 4 post-linguistic children have environmental sound awareness, detection of instrumental sounds and lip-reading enhancement; 3 pre-linguistic and 2 post-linguistic children achieved bi-syllabic word recognition as well as understanding of simple commands, but only one post-linguistic child had open set recognition (average 50% correct responses) and can perform the speech tracking test. Cognitive testing in a subset of 9 children using the ABI demonstrated improved selective visual-spatial attention (form completion subtest) and fluid (multisensory) reasoning (repeated patterns subtest) when compared to a group of 4 congenitally deaf children without an auditory assistive device.

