Children receiving the ABI in the present study have a very realistic chance for gaining improved sound awareness, enhanced lip reading, and limited closed set speech (pattern perception) understanding with the device. This has been previously demonstrated for both adults (>18 yrs of age) with and without NF2 as well as for children (<18 yrs) without NF2. In most instances, this will represent a significant improvement over that obtained using their CI. Higher levels of closed set (words) and open set speech understanding have been demonstrated in some adults and children using the ABI. As age of implantation and the presence of developmental and cognitive delays negatively impact upon a child’s ability to achieve this level of performance, the chances of this outcome for children in the present study remain unknown since most of those implanted in other parts of the world had these complicating, negative prognostic factors. This study will actively control for these variables by only implanting younger (18 mo to 5 yrs) pre-linguistic children without such delays or those that are post-linguistic (< 18 yrs with previous open-set speech perception using a cochlear implant). Our group at UNC as well as others has personally tested children that have obtained significant open-set speech perception abilities using the ABI alone (implanted in Italy). As in CI, increased speech perception abilities can improve speech and language acquisition, educational achievement, employment opportunities and quality of life. These long-range benefits very much depend on the speech perception abilities of the child using the ABI device. If the device fails to provide sound awareness or improved speech understanding, then the remaining benefits are much less likely.

Potential Risks (see “Complications from Auditory Brainstem Implantation” for a literature review)

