This study is an early feasibility study of the Nucleus 24 ABI in children without NFII. It will be conducted as a repeated-measures, single subject experiment with up to 10 replications (i.e. 10 total subjects). A single-subject research design was chosen (in which each subject serves as their own control) in order to accommodate the heterogeneity that is well known to characterize auditory prosthesis research. Post-operative evaluations will be conducted at the initial activation and at 1, 3, 6, 12, 18, 24, 30, and 36-month intervals post-activation. A 36-month follow-up was chosen in an effort to demonstrate the emergence of open-set speech perception abilities prior to study cessation. Experience in the CI literature has shown that a minimum of 2 years of device usage is required for children with pre-lingual hearing impairment to develop some open-set speech perception abilities (50). Blinding or masking procedures are not included in the design, as the presence/absence of a brainstem implant cannot be easily concealed from the device recipients and/or clinical investigators.

Preoperative measures will include high-resolution brain MRI, temporal bone CT and standardized, developmentally appropriate audiological and speech and language development test batteries. Children between 18 mo and 5 yrs of age with one of the anatomic conditions mentioned below and a present and patent cochlea will have previously received a CI as a precondition prior to consideration and will have demonstrated very limited to no benefit from

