the device based on a lack of development of significant closed set (more than pattern perception) or open set speech perception, and failure to achieve developmentally appropriate language growth during the follow up period. Those without a present or patent cochlea will be implanted with the ABI without the need for previous CI. Post-linguistic children (<18 yrs) will have had a CI but lost or lacked benefit from an appropriate CI and have no potential for revision CI surgery to improve their condition. The side/ear contralateral to the previous placed CI will be chosen, unless not possible (eg. bilateral CIs), to avoid potentially same-side, unwanted surgical and processor interactions as well as to allow comparison of performance in the follow-up period. If ABI needs to be considered ipsilateral to the previous CI, removal of the CI will need to be considered. Surgical interaction would be the issue of needing to operate in and around the CI device putting it at risk of damage. Unwanted processor interactions would be problematic if the receiver stimulator of the previous CI and the ABI were located in the same region. The ABI processor headpiece might be attracted to the CI receiver stimulator.

Following implantation of the investigational device and at least 4-6 weeks of healing, the ABI will be activated in a controlled setting and auditory performance assessed at the previously proposed intervals (1, 3, 6, 12, 18, 24, 30, 36 months). Subjects will be evaluated using the Nucleus Speech Processor and programmed with an approved sound processing strategy. Post-operative auditory function will be evaluated using behavioral audiometry and commonly used, developmentally appropriate measures of speech perception, speech production and language. Auditory function will also be assessed using electrophysiological tests at appropriate intervals.

SPECIFIC AIMS

Aim 1: Demonstrate the safety of ABI surgery in children.

Aim 2: Demonstrate the development of sound awareness and improved speech understanding among children implanted with the ABI when compared to their baseline skills.

Aim 3: Demonstrate the development of oral language skills following the use of the ABI that were not evident prior to its use.

Methods and Subjects

Up to 10 subjects will be enrolled in the study at the sponsoring location. Qualified subjects must meet the following inclusion criteria and must not exhibit any of the exclusion criteria.

Inclusion Criteria

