- Pre-linguistic hearing loss (birth-5 yrs.; age at ABI 18 months-5yrs) with both:
 - MRI +/- CT evidence of one of the following:
 - Cochlear nerve deficiency
 - Cochlear aplasia or severe hypoplasia
 - Severe inner ear malformation
 - Post-meningitis ossification
 - When a cochlea is present or patent, lack of significant benefit from CI despite consistent use (≥ 6 mo.)
 - No or limited speech perception ability (limited to pattern perception on closed set testing materials using the CI)

- Lack of progress in auditory skills development

18 months of age was chosen for the lower age limit to minimize the adverse effects of auditory deprivation on speech perception, speech production, and language development (23, 50). Moreover, 18 months of age will allow for a child to receive a CI at 1 year of age and have at least 6 months of device experience prior to considering ABI. Six months of CI usage prior to ABI consideration was chosen as this time period to allow for clear demonstration of lack of benefit as defined as either: (1) lack of sound awareness, or (2) where elevated charge requirements, absent ECAPs, elevated pure tone averages (>45 dB), and no or limited speech perception abilities are evident. To determine if a child is making significant progress both subjective and objective measures are used. Objectively, standardized speech perception, production, and language tests (as described below) are administered to determine if standard scores are following typical developmental patterns, even at a reduced rate. No or limited speech perception abilities will be considered when there are no improvement in IT-MAIS, or ESP measures from preop measures at the 6 month post-CI interval (30, 50). Developmental norms are also determined based on the hearing age. For example, a child who is 9 months old receptively understands between 3 and 50 vocabulary words and approximately 300 between the ages of 2 and 3. Does the child with a hearing age of 9 months understand this many words? For early speech development, all English vowels should be present by a hearing age of 12 months. Children 18 months of age can be tested using the standardized measures to determine progress.

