From a surgical perspective, 18 months of age is a sufficient size and weight in most instances to consider ABI surgery. Factors that increase the anesthetic risk (particularly cardiac arrest) among children undergoing surgery include: age < 1 yr, obesity, other associated co-morbidities, ASA-PS ≥ 3 , emergency surgery. Moreover, children undergoing elective surgery should be free of upper respiratory tract infection to reduce the risk of respiratory tract complication. Importantly, it is currently standard practice to undertake CI between 1 and 2 years of age. The risk for anesthetic-related complications will be no different for this proposed group of children undergoing ABI surgery (58). While not specifically studied, the risk of major blood loss from ABI surgery is relatively small since tumor resection is not needed. If Chiari posterior fossa decompression surgery among children serves as a surrogate for blood loss risk in this population, a recent meta-analysis suggested only 1 of 246 children experienced any bleeding related complication from this type of surgery (59). As stated below, children with any medical co-morbidities that place them at an increased risk for complication will be avoided in this trial.

- Post-linguistic hearing loss (<18 yrs. of age) with both:
 - Loss or lack of benefit from appropriate CI without the possibility for revision or contralateral implantation. Examples might include:
 - Post-meningitis ossification
 - Bilateral temporal bone fractures with cochlear nerve avulsion
 - Failed revision CI without benefit
 - Previously developed open set speech perception and auditory-oral language skills
- No medical contraindications
- Willing to receive the appropriate meningitis vaccinations
- No or limited cognitive/developmental delays which would be expected to interfere with the child's ability to cooperate in testing and/or programming of the device, in

- developing speech and oral language, or which would make an implant and subsequent emphasis on aural/oral communication not in the child's best interest
- Strong family support including language proficiency of the parent(s) in the child's primary mode of communication as well as written and spoken English.
- Reasonable expectations from parents including a thorough understanding:
 - of potential benefits and limitations of ABI
 - of parental role in rehabilitation

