It is anticipated that this pilot study will be used to demonstrate safety and give some idea regarding efficacy. However, a larger scale clinical trial will be needed beyond the pilot study to demonstrate surgical safety on a broader scale (across surgeons and institutions) and the utility of the device for the intended auditory benefits. Ten subjects should be a sufficient sample size to demonstrate safety. If the European data is correct regarding complication rates in children, a single CSF leak might occur in one subject and non-auditory side effects can be expected to occur in roughly 20% of children or 2 subjects in this study. This number seems to be a conservative and reasonably small number to demonstrate these effects. Non-auditory stimulation is not serious and can be programmed around with simple changes in device programming during activation. For speech perception and production, the within subject design should allow us to see some benefit from the device if effective. Since the children are deaf, any development of significant open or closed set perception (beyond patten perception) would be attributable to the device. Similarly for language outcomes although these will take longer time to develop. Thus, the safety numbers are the drivers in powering this study.

The data will be recorded in patient-specific binders on a case-by-case basis after each subject encounter. All data will be entered in to the secure, File Maker Pro, customized database for CI research housed in the Department of Otolaryngology-Head and Neck Surgery that is currently in use. The lead investigator will cross check the data prior to approval for review. The data will be exported by desired fields to an Excel spreadsheet (Microsoft) for further analysis. Statistics will be carried out using SPSS software. If needed, statistical consultation will be sought at the University TRACS or Odum Institute.

Study Endpoints

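### The maximum number of children is 15 in the purpose statement but 10 in the design, enrolment and sample-size text

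*Combined protocol and SAP*

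**What the plan says.** The opening purpose statement reads: "This study proposes to implant up to 10 pre-linguistic young children (18 mos to 5 yrs. of age) and 5 post-linguistic children". It describes the two groups separately and joins them with a plain conjunction. It gives no overall total.

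Three later places use 10:

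- Protocol (design paragraph): a repeated-measures, single-subject experiment "with up to 10 replications (i.e. 10 total subjects".
- Methods and Subjects: "Up to 10 subjects will be enrolled in the study at the sponsoring location".
- Data and Analysis (sample-size paragraph): "Ten subjects should be a sufficient sample size to demonstrate safety". The same paragraph expects non-auditory side effects in about 20% of children, which it equates with 2 subjects. It allows for one CSF leak and concludes that safety determines the size of the study.

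The later text covers both cohorts. The Protocol section goes on to say "Post-linguistic children (<18 yrs) will have had a CI but lost or lacked benefit from an appropriate CI". The Inclusion Criteria, which follow directly from the enrolment cap, list "Pre-linguistic hearing loss (birth-5 yrs.; age at ABI 18 months-5yrs) with both" and then "Post-linguistic hearing loss (<18 yrs. of age) with both". Potential Benefits describes the eligible population as "only implanting younger (18 mo to 5 yrs) pre-linguistic children without such delays or those that are post-linguistic".

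**The concern.** A reader of the purpose statement would conclude that up to 15 children may be implanted. A reader of the design, enrolment or sample-size text would conclude 10. All four statements are current text.

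The maximum N in this study is a limit on how many children undergo retrosigmoid craniotomy with an electrode array placed on the brainstem. It is also the figure on which the protocol rests its size, since Data and Analysis says that safety drives it. If the limit is ambiguous, the investigators, the IRB and the two external reviewers cannot tell whether an eleventh child is within the plan. Children 11 to 15 would have no stated justification, because the sample-size argument is written only for ten.

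**Working it through.** **Inputs**

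| Place | Maximum stated | Cohorts covered |
|---|---|---|
| Purpose statement | 10 pre-linguistic and 5 post-linguistic | both, listed separately |
| Protocol, design paragraph | 10, called the total | both (post-linguistic children described in the same section) |
| Methods and Subjects | 10 | both (criteria for each follow) |
| Data and Analysis | 10 | not restricted to one cohort |

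**Step 1: the plan's own figure.** Data and Analysis equates about 20% with 2 subjects. Expected count = N × rate = 10 × 0.20 = 2. This reproduces the stated figure, so that paragraph was written for N = 10.

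**Step 2: the purpose statement.** 10 + 5 = 15. Difference: 15 − 10 = 5 children. Relative to the cap: 5 / 10 = 50%.

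**Step 3: the same count at 15.** 15 × 0.20 = 3, not 2. This is only supporting evidence, because the rate is approximate. The summary of risks under Human subject protection measures puts it below 20% in children, and 2 / 15 = 13% would fit that.

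**Step 4: can the figures be read together?**

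- *The 10 is the pre-linguistic group only.* The design text that gives the total goes on to describe post-linguistic children, and the criteria under the cap admit both groups. This reading fails.
- *The 5 are part of the 10.* The purpose statement contains nothing that makes the second group a subset of the first. This reading fails on the wording.
- *The 10 is a cap for one site.* Methods and Subjects does mention the sponsoring location, and the criteria speak of investigation sites in the plural. But the design paragraph calls 10 the total. This reading fails.
- *The purpose figures are ceilings per cohort within a total of 10.* This is possible as an intention, but it is not written, and no available text divides the 10.

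**Step 5: scale of the difference.**

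- One CSF leak is 1 / 10 = 10% of ten children or 1 / 15 = 6.7% of fifteen. These are shares only; the sample-size paragraph states no leak rate.
- For illustration, and not a planned analysis: if a complication is seen in no child, the one-sided 95% upper limit for its rate is 1 − 0.05^(1/n). For n = 10 this is 25.9%; for n = 15 it is 18.1%.
- Study Endpoints expects 1 to 3 recruits a year. Five more children would take 5 / 3 = 1.7 to 5 / 1 = 5 further years.

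**The case against.** The best defence is that the plan is clearer than the contradiction suggests. Three places, including the operative enrolment sentence and the only sample-size argument, agree on 10. The purpose statement is introductory, nowhere prints 15, and may simply give a ceiling for each cohort. Because every figure is qualified as a maximum, the final denominator is open under either number. No analysis or stopping threshold depends on the choice: safety is judged case by case, and at 1 to 3 recruits a year an eleventh child would not arrive before the fourth year.

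Much of this is fair, and it limits the point. The majority of the text favours 10, and the consequence is not analytic. Three smaller cautions also stand:

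- Potential Benefits restricts who may be implanted but does not commit the study to implanting both groups. The argument therefore rests on the design text and the inclusion criteria.
- The CSF percentages are not planned rates. Table 2 shows no leak among non-tumor children, and Potential Risks says only that the risk will be well below 10%.
- The expected count of 3 at N = 15 holds only if 20% is kept.

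None of this removes the conflict. A reading that needs an unstated qualification in the purpose statement is a reason to write that qualification down. A majority of statements does not tell the investigators which limit applies.

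**Conclusion.** The concern holds. The plan's maximum sample size is contradictory: 15 by the purpose statement, 10 by the design, enrolment and sample-size text, a difference of 5 children or 50% of the cap. The conclusion rests on the wording alone. The 20% calculation supports it but is not needed, and the zero-event limits only show scale.

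The documents do not settle which total is intended. Some pages were not in the text available for review, but even if one of them addresses the number, the four statements would still disagree as written. The consequence is confined to the maximum number of children exposed to surgery and the denominator behind the safety justification; no planned test changes. It should be corrected.

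**What to change.** The sponsor should confirm which maximum applies. It should then state that one number, with its pre-/post-linguistic split or a maximum for each cohort, in the same terms in the purpose statement, the Protocol design paragraph, Methods and Subjects, and Data and Analysis.

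- **If 10 is confirmed:** correct the purpose statement and add the split. The expected counts in Data and Analysis can stay. The cost is wording only.
- **If 15 is confirmed:** correct the other three places. Restate the expected number of non-auditory side effects with the rate assumed (3 rather than 2 if 20% is kept), and say whether the allowance for one CSF leak still applies.

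The correction itself adds no visits, tests or analyses. Confirming 15 would, however, raise the current enrolment cap by 5 children. Each would have surgery, activation and eight scheduled visits from month 1 to month 36, so up to 5 × 8 = 40 further visits, with the longer recruitment shown above.
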